8.4 Data Quality Assurance

The DMP will describe structures, processes, policies and procedures employed to ascertain the quality of the data and to ensure against errors in data entry, transfer or transformation accuracy throughout the study. Data quality oversight will involve a multi-tiered process that includes electronic edit check specifications, manual checks, self-evident corrections, listing reviews and electronic data transfer agreement summaries. Electronic edit checks will be programmed to show discrepancies online at the time of data entry, giving the operator the option to confirm acceptance of the discrepant data or change the data. Manual review and listing reviews will be run as outlined in the DMP, either at predetermined intervals or as necessary. The CDM will

open queries to resolve any discrepancies either within the database or directly with study personnel. All changes to existing data will be fully tracked, maintaining an audit trail report of every transaction.

9 STUDY MANAGEMENT

9.1 Regulatory and Ethical Consideration

All study activities will be conducted in accordance with regulatory guidelines for real-world, pragmatic research. Study personnel at physician sites will be provided training on the study protocol, the ICF, data collection and data entry to ensure both the protection of potential study patients as well as the scientific integrity of the study. A hybrid approach of both remote and onsite monitoring will be employed.

9.1.1 IRB/Independent Ethics Committee (IEC)

The study physician will have prospective approval of the study protocol, ICF and any patient information or recruiting materials, if applicable, prior to commencement of any study activities. In the case of a protocol amendment, the study physician must sign the revised protocol and submit the amendment to the IRB/IEC for review and approval prior to implementation of any changes specified in the protocol amendment. All changes in research activity and all unanticipated problems involving risk to human patients or others must be reported promptly to the IRB/IEC.

The study physician will obtain continued review of the study at intervals not to exceed one year or otherwise specified by the IRB/IEC.

9.1.2 Informed Consent

An ICF fully describing the purpose, procedures and potential risks and benefits of the study will be developed and approved by the IRB/IEC prior to study initiation. The study physician must ensure that each study patient is fully informed of the study and authorizes release of health information prior to study enrollment. The study physician, or study personnel designated by the study physician, will obtain written informed consent from each patient prior to initiation of any study-related procedures. Each patient will be given a copy of the signed ICF. The study physician will retain the original signed ICF for each patient.

The IRB/IEC must prospectively approve the ICF and any changes to the ICF during the course of the study before use. If a protocol amendment alters the study design or increases the potential risk to the patient, the ICF must be revised and submitted to the IRB/IEC for review and approval prior to implementation. The revised ICF must then be used to obtain consent from new patients entering the study. The revised ICF must also be used to obtain consent from currently enrolled patients if they are affected by the amendment.

9.2 Dropouts

Patient participation is strictly voluntary and patients may refuse to participate or withdraw from the study at any time and for any reason. As such, patients may voluntarily withdraw prior to completing the final visit. In such cases, the study physician will document the specific reason for the incomplete information (e.g., withdrawal of consent, lost to follow-up) on the eCRF. The physician should continue follow-up with the patient for any unresolved SAEs.

9.3 Record Retention and Access

This study may be subject to audits or evaluations by regulatory authorities or Boehringer Ingelheim (or its designee). To enable such evaluations and/or audits, the study physician must agree to maintain and allow reasonable access to required patient and study records. The study physician agrees to keep the identity of all participating patients (sufficient information to link records, e.g., hospital records), all original signed ICFs, SAE Forms, source documents, and detailed records of treatment disposition, and adequate documentation of relevant correspondence (e.g., letters, meeting minutes, telephone calls, reports). The study physician should retain records according to local regulations, or as specified in the Clinical Study Agreement, whichever is longer.

10 PUBLICATION OF STUDY RESULTS

All information related to this study is considered confidential information belonging to Boehringer Ingelheim and [REDACTED] A final study report will be generated following completion of data collection and analysis. Results and findings will be submitted to conferences and for publication in peer-reviewed scientific journals.

Table 1: Time and Events Schedule

Assessment or Procedure	Study Visits		
	Baseline	On Study Follow-Up¹	EOS 12 Months
Written Informed Consent	X		
Eligibility Criteria	X		
Randomization	X		
Demographics	X		
Selected pre-specified comorbid conditions	X		
CBC (Baseline Blood Eosinophil Count Required) ²	X		
Smoking Status	X		
COPD Diagnosis Date	X		
COPD Exacerbation History (number and severity of exacerbations in last year)	X		
Pre-Study COPD Therapy	X		
Reason for therapy escalation	X		
COPD Concomitant Medications	X	X	X
CAT TM	X		
Study Treatment	X	X	X
COPD Exacerbations		X	X
Selected AEs ³		X	X
SAEs ³		X	X

¹The only required study visits are Baseline and EOS. Data will be collected at routine clinical visits and other patient contact in between Baseline and EOS if available per standard clinical practice.

²In the event that a CBC is not available at baseline, laboratory results within 12 months of baseline will be accepted.

³All SAEs and selected AEs will be collected from Baseline through EOS or early termination of study participation. Selected AEs are AEs leading to study treatment discontinuation, dose modification or trial withdrawal.

Table 2: Sample size calculations (with number of events) under different assumptions for p1, HR and power, 20% non-inferiority margin, one-sided alpha 0.025 and 15% drop-out rate during 12 months.

Scenario	P1 (proportion of patients with >=1 moderate/severe COPD exacerbation during 12 months in Triple Therapy arm)	P2 (proportion of patients with >=1 moderate/severe COPD exacerbation during 12 months in Stiolto arm)	Expected HR of moderate/severe COPD exacerbations between Stiolto and Triple Therapy	Power	Number of events (moderate/severe COPD exacerbations)	Sample size (total)
1	40%	39.07%	0.97	95%	1147	3120
2	42.5%	42.5%	1	90%	1264	3200
3	45%	46%	1.03	80%	1358	3204

These sample size calculations were completed using Addplan 6.1 software based on a non-inferiority test for survival analysis.

APPENDIX A: COPD Assessment Test™ (CAT)

Your name: _____

Today's date: _____

How is your COPD? Take the COPD Assessment Test™ (CAT)

This questionnaire will help you and your healthcare professional measure the impact COPD (Chronic Obstructive Pulmonary Disease) is having on your wellbeing and daily life. Your answers, and test score, can be used by you and your healthcare professional to help improve the management of your COPD and get the greatest benefit from treatment.

For each item below, place a mark (X) in the box that best describes you currently. Be sure to only select one response for each question.

Example: I am very happy 1 2 3 4 5 I am very sad

						SCORE				
I never cough			0	1	2	3	4	5	I cough all the time	
I have no phlegm (mucus) in my chest at all			0	1	2	3	4	5	My chest is completely full of phlegm (mucus)	
My chest does not feel tight at all			0	1	2	3	4	5	My chest feels very tight	
When I walk up a hill or one flight of stairs I am not breathless			0	1	2	3	4	5	When I walk up a hill or one flight of stairs I am very breathless	
I am not limited doing any activities at home			0	1	2	3	4	5	I am very limited doing activities at home	
I am confident leaving my home despite my lung condition			0	1	2	3	4	5	I am not at all confident leaving my home because of my lung condition	
I sleep soundly			0	1	2	3	4	5	I don't sleep soundly because of my lung condition	
I have lots of energy			0	1	2	3	4	5	I have no energy at all	
										TOTAL SCORE 

[figure not shown]
COPD Assessment Test and CAT logo is a trademark of the [REDACTED] group of companies.
© 2009 [REDACTED] All rights reserved.

Summary of Amendments and Updates**Summary of Changes**
1237-0064 Protocol Version 2.0, dated 09May2018

Number	Section/Page	Change	Rationale
1	Global Change	May 9, 2018 June 7, 2017 Version 12 .0	Updated protocol date and version.
2	Study Approvals, page 2	Sponsor Approval: Name: [REDACTED] Title: [REDACTED] of Clinical Development & Medical Affairs, Primary Care - Respiratory COPD & Asthma [REDACTED]	Updated sponsor Principal Investigator for study approval signature.
3	Synopsis Study Procedures, page 9	
 • A complete blood count (CBC) including differential white cell count will be drawn at baseline. In the event that a CBC is not available at baseline, laboratory results within 12 months of baseline will be accepted. 	Added language to relax the timing required for a baseline CBC. This change increases the flexibility of study requirements and is consistent with the pragmatic design.
4	Section 4 Study Design 4.2.2 Participant Recruitment and Eligibility, page 17-18	To maintain the real world nature of the study, patients will be recruited for enrollment when they interact with their physician as part of their standard care.	Removed sentence to allow additional patient outreach at study sites to increase study enrollment.
5	Section 4 Study Design	To enhance enrollment at trial initiation, up to 500 non-[REDACTED]	Deleted sentences to remove any restriction from

	4.2.2 Participant Recruitment and Eligibility, page 18	patients will be allowed to enroll, following which enrollment will be restricted to [REDACTED] patients only if possible. In such event that additional non-[REDACTED] patients are needed to complete enrollment, the decision to re-open enrollment to non-[REDACTED] patients will be made jointly between [REDACTED] and Boehringer Ingelheim.	enrollment of non-[REDACTED] patients to increase study enrollment.
6	Figure 1: Schematic of Study Design, page 20	
 Identify Eligible patients interacts with physician in course of normal care 	Modified sentence to allow additional patient outreach at study sites to increase study enrollment, consistent with change #4 in 4.2.2 above
7	Section 5 Study Procedures 5.2 Baseline Visit, page 21	A blood sample will be drawn at the baseline visit for a complete blood count (CBC) including differential white cell count. In the event that a CBC is not available at baseline, laboratory results within 12 months of baseline will be accepted.	Added language to relax the timing required for a baseline CBC. This change increases the flexibility of study requirements and is consistent with the pragmatic design.

# List of Abbreviations

| Abbreviation or
Special Term | Definition  |  |  |
|---------------------------------|---|--|--|
| AE                              | Adverse Event   |  |  |
|                                 |   |  |  |
| AIRWISE                         | A ssessment In a R eal W orld setting of the effect of Inhaled
S teroid-based triple therapy versus the combination of
tiotropium and olodaterol on reducing COPD E xacerbations |  |  |
| CAT                             | COPD Assessment Test  |  |  |
| CBC                             | Complete Blood Count  |  |  |
|                                 |   |  |  |
| CI                              | Confidence Interval   |  |  |
| СМН                             | Cochran-Mantel-Haenszel   |  |  |
| COPD                            | Chronic Obstructive Pulmonary Disease   |  |  |
| eCRF                            | Electronic Case Report Form   |  |  |
| EDC                             | Electronic Data Capture   |  |  |
| E&M                             | Evaluation and Management   |  |  |
| EOS                             | End of Study  |  |  |
| ER                              | Emergency Room  |  |  |
| FDC                             | Fixed Dose Combination  |  |  |
| GERD                            | Gastroesophageal Reflux Disease   |  |  |
| GLM                             | General Linear Model  |  |  |
| GOLD                            | Global Initiative for Chronic Obstructive Lung Disease  |  |  |
|                                 |   |  |  |
|                                 |   |  |  |
| HR                              | Hazard Ratio  |  |  |
| ICD-10                          | International Classification of Diseases, Tenth Revision  |  |  |
| ICD-10-CM                       | International Classification of Diseases, Tenth Revision,
Clinical Modification  |  |  |

| Abbreviation or
Special Term | Definition                                   |
|---------------------------------|--|
| ICS                             | Inhaled Corticosteroid                       |
| IPV                             | Important Protocol Violations                |
| IQR                             | Interquartile Range                          |
| ITT                             | Intent to Treat                              |
| LABA                            | Long-Acting Beta Agonist                     |
| LAMA                            | Long-Acting Muscarinic Antagonist            |
| LOS                             | Length of Stay                               |
| MedDRA                          | Medical Dictionary for Regulatory Activities |
| OCS                             | Oral Corticosteroid                          |
| OV                              | Office Visit                                 |
| PDE4                            | Phosphodiesterase 4                          |
| РР                              | Per Protocol                                 |
|                                 |  |
|                                 |  |
| РТ                              | Preferred Term                               |
| RR                              | Risk Ratio                                   |
| SABA                            | Short-Acting Beta Agonist                    |
| SAE                             | Serious Adverse Event                        |
| SAMA                            | Short-Acting Muscarinic Antagonist           |
| SAP                             | Statistical Analysis Plan                    |
| SD                              | Standard Deviation                           |
| SM                              | Service Mark                                 |
| SMQ                             | Standardized Medical Queries                 |
| SOC                             | System Organ Class                           |
| T1DM                            | Type 1 Diabetes Mellitus                     |
| T2DM                            | Type 2 Diabetes Mellitus                     |
| TM                              | Trademark                                    |

# **1.0 INTRODUCTION**

The background and rationale for this study can be found in the introduction to the study protocol (Section 1).

#### 2.0 STUDY OBJECTIVES

The primary, secondary

[figure not shown]
Section 2, Study Objectives).

[figure not shown]
# 2.1 Changes in the Planned Analysis of the Study

Due to slower than expected enrollment despite mitigation efforts, a business decision was made to discontinue enrollment of new patients in the trial after the end of August 2019. Active patients will continue and any patient that is already randomized into the trial shall continue through the planned 12 months of the trial.

As a result of this early stopping and the limited sample size enrolled by the end of August 2019 (approximately 703 patients instead of the planned 3200 patients), the trial will be underpowered, therefore the null hypothesis of non-inferiority of Stiolto Respimat to Triple therapy as measured by time to first moderate or severe exacerbation will not be tested. No statistical inference will be done (i.e., no comparison with the NI margin, no calculation of p-value). Models, such as the Cox proportional hazards model and the negative binomial, will still be run on the ITT population to estimate the hazard ratio, rate ratio and confidence intervals.

Some changes were made to the thresholds for baseline blood eosinophil level, in sections 4.4.7, 4.4.8, 4.5.4.3 and 5.5.1, to reflect current GOLD recommendations.

After further review, due to the low number of patients and events, and the strong knowledge base Boehringer Ingelheim (BI) have for Stiolto, the safety team decided that the additional custom Boehringer Ingelheim searches which are standardized for relevant topics in COPD studies are optional. Therefore the following analyses will not be performed in Section 6.4.1: summary tables and listings to compare the incidence of AEs across treatment groups by medical concept (MedDRA Standardized Medical Queries (SMQ) or custom Boehringer Ingelheim searches which are standardized for relevant topics in COPD studies.

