While the benefits of ICS therapy are well documented across a broad spectrum of patients with asthma, their benefits in the COPD population appear to be more targeted to select patient phenotypes. Specifically, the benefit appears to be most robust in patients with severe COPD with a history of frequent exacerbations or with an inflammatory/allergic component to their disease. In addition, ICS therapy is associated with localized symptoms such as voice hoarseness and thrush, as well as systemic diseases such as upper respiratory tract infections and osteoporosis.

The Withdrawal of Inhaled Steroids during Optimized Bronchodilator Management (WISDOM)⁸ trial explored the impact of withdrawing ICS in patients concurrently receiving LAMA/LABA combination therapy. In this randomized, double-blind, non-inferiority designed study the risk of moderate or severe exacerbations was similar between those who had their ICS withdrawn versus those who continued. A logical follow-up research question from the WISDOM study is to assess patients who are not controlled on their current therapy of ICS-LABA, LABA alone or LAMA alone, to see if change in therapy to LAMA/LABA FDC therapy is similar in effect to triple therapy. Studying the question in a manner that assesses patients as therapy is “stepped-up” is reflective of usual clinical practice and would provide valuable and relevant real-world evidence to both practicing clinicians and health care payers. In addition, the GOLD 2017 update specifically states that “more evidence is needed to draw conclusions on the benefits of triple therapy LABA/LAMA/ICS compared to LABA/LAMA.” To this end, the proposed study, AIRWISE: Assessment In a Real World setting of the effect of Inhaled Steroid-based triple

⁸ Magnussen H, Disse B, Rodriguez-Roisin R, et al. Withdrawal of Inhaled Glucocorticoids and Exacerbations of COPD. N Engl J Med. 2014;317:1285-94.

therapy versus the combination of tiotropium and olodaterol on reducing COPD Exacerbations, is a non-inferiority trial of community-based COPD patients randomized to either Stiolto Respimat or triple therapy following a physician decision to escalate therapy. The decision to escalate therapy will be at the discretion of the treating physician. Patients will be treated according to routine clinical practice and followed for clinical (exacerbations, etc.) [REDACTED]

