6.6 Safety Analysis

[figure not shown]
Collection of AEs in the study eCRF will be limited to AEs leading to study treatment discontinuation or dose modification, or trial withdrawal. All SAEs will be reported by the investigator via a dedicated SAE report form directly to Boehringer Ingelheim Global Pharmacovigilance as described in [section 7.2](#). As hospitalization SAEs are reflected in claims records, a patient-level review comparing hospitalization claims entries with reported SAEs for each respective patient will take place after completion of the 12-month visit in order to identify any hospitalizations of which the investigator was potentially unaware. The investigator will receive information of any SAE identified through this process and report it using the standard SAE reporting process (See [section 7.2](#)).

SAE data for analysis will be drawn from the Boehringer Ingelheim Safety Database.

Analysis of non-serious AEs (leading to study treatment discontinuation or dose modification, or trial withdrawal) will be performed on the study database, as these are entered in the eCRF only.

Safety analyses will be descriptive in nature. No hypothesis testing is planned prospectively.

AEs will be coded using the current version of the Medical Dictionary for Regulatory Activities (MedDRA) coding dictionary at the time of reporting, and recoded to the MedDRA version current at the time of database integration. Summary tables and listings will be produced to compare the incidence of AEs across treatment groups, by Preferred Term (PT)/System Organ Class (SOC) and also by medical concept (MedDRA Standardized Medical Queries (SMQ) or custom Boehringer Ingelheim searches termed Pharmacovigilance (PV) endpoints). All AEs with an onset after the first dose of trial medication and up to 21 days after the last dose of trial medication will be assigned to the on-treatment period. Other AEs will be assigned either to the screening period, post-treatment period or the post-study period as appropriate.

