# 6.4.1 AE Analysis

AE analyses will be descriptive in nature. No hypothesis testing is planned prospectively. All analyses of AEs will be based on the number of patients with AEs and NOT on the number of AEs.

SAE data will be drawn from the Boehringer Ingelheim Safety Database, while other AEs collected as per protocol through the eCRF will be drawn from the study database. AE data for analysis will be merged from all sources for analysis.

AEs will be coded using the current version of the Medical Dictionary for Regulatory Activities (MedDRA) coding dictionary at the time of reporting. Summary tables and listings will be produced to compare the incidence of AEs across treatment groups, by Preferred Term (PT)/System Organ Class (SOC).

The frequency and percentage patients experiencing AEs and SAEs will be summarized by SOC and PT for the safety population overall and by treatment group as follows:

- All collected AEs, regardless of seriousness, relatedness, or collection context
- AEs leading to study treatment discontinuation, dose modification or trial withdrawal
- AEs leading to study treatment discontinuation (subset of the above table)
- AEs with a reasonable causal relationship to study treatment
- All SAEs
- Fatal AEs (subset of all SAEs)
- Listing of all SAEs

There will be no subgroup analyses for safety.

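### SAP 2.1 cancels every medical-concept AE summary, SMQs included, for reasons that do not cover the ICS-containing arm; a short ICS-related grouped table should stay

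*SAP*

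**What the plan says.** Protocol 6.6 plans tables and listings that compare AE incidence between arms by PT and SOC, "and also by medical concept (MedDRA Standardized Medical Queries (SMQ) or custom Boehringer Ingelheim searches termed Pharmacovigilance (PV) endpoints").

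SAP 2.1 changes this. Its reasons are "due to the low number of patients and events, and the strong knowledge base Boehringer Ingelheim (BI) have for Stiolto". On that basis the safety team decided that "the additional custom Boehringer Ingelheim searches which are standardized for relevant topics in COPD studies are optional". The next sentence concludes that "the following analyses will not be performed in Section 6.4.1", and the item it names is the set of tables and listings "by medical concept (MedDRA Standardized Medical Queries (SMQ) or custom Boehringer Ingelheim searches which are standardized for relevant topics in COPD studies".

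SAP 6.4.1 shows what is left. AEs and SAEs "will be summarized by SOC and PT for the safety population overall and by treatment group". The tables cover all collected AEs, AEs leading to discontinuation, dose modification or withdrawal, related AEs, SAEs and fatal AEs. There is also a listing of all SAEs. The section bases every AE analysis on the number of patients, not the number of events.

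Two other places matter. Protocol 1.1 says that "ICS therapy is associated with localized symptoms such as voice hoarseness and thrush, as well as systemic diseases such as upper respiratory tract infections", and then adds osteoporosis. Protocol 6.6 limits non-serious AEs in the eCRF to those leading to treatment discontinuation, dose modification or trial withdrawal. Both documents make safety descriptive, with no hypothesis test.

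**The concern.** The trial compares a dual bronchodilator with a regimen that adds an ICS, and the protocol's own background names the harms it associates with ICS. A reader weighing the two regimens will want to see those harms by arm, in groups that make clinical sense. SAP 2.1 removes the only planned summary that could group them that way.

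The reasons given do not support a cut of that extent. Only the custom searches are called optional, yet the SMQs go too. Product knowledge is claimed for Stiolto alone. The remaining reason, few patients and events, would normally lead a statistician to pool related terms, because single-term rows become too thin to read.

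At stake is the readability of the serious and treatment-changing ICS-related events, respiratory infection above all. No primary or secondary endpoint is affected.

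**Working it through.** **1. Is the low-number reason true?** Yes. Protocol Table 2, scenario 2, gives 1264 events and 3200 patients, and both reproduce.

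- Events = 4(1.960 + 1.2816)² / (ln 1.2)² = 1264.4.
- Probability of an observed event, with exponential event (42.5%) and drop-out (15%) hazards over 12 months: λ = −ln 0.575 = 0.5534 and μ = −ln 0.85 = 0.1625, so P = λ/(λ+μ) × (1 − e^−(λ+μ)) = 0.395.
- N = 1264 / 0.395 ≈ 3198, against 3200 stated.
- At the 703 patients in SAP 2.1, expected primary events are 703 × 0.395 ≈ 278, and power at the 1.20 margin is about 33%.

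**2. What does each reason cover?**

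- Low numbers: both arms, and both SMQs and custom searches.
- Knowledge of Stiolto: one arm. Nothing is said about ICS or triple therapy.
- Called optional: the custom searches only. No separate reason is given for the SMQs.

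**3. Which way do low numbers point?** The documents give no AE rates, so every count here is assumed. Take 351 triple-therapy and 352 Stiolto patients (703 at 1:1). For the risk ratio (RR), SE(ln RR) = √(1/a − 1/n₁ + 1/b − 1/n₂).

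- One grouping, 24 v 12: RR = (24/351)/(12/352) = 2.01; SE = √(0.0417 − 0.0028 + 0.0833 − 0.0028) = 0.345; 95% CI 1.02 to 3.95.
- The same patients split evenly over three PTs without overlap, 8 v 4 per row: RR = 2.01; SE = √(0.1250 − 0.0028 + 0.2500 − 0.0028) = 0.608; 95% CI 0.61 to 6.60.

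A second set of assumptions uses 351.5 per arm and a true doubling in the triple arm. The factor is what the RR is multiplied and divided by to give its 95% limits.

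| Assumed rates | Expected patients | Factor |
|---|---|---|
| 0.5% v 0.25% | 1.8 v 0.9 | 12.9 |
| 1.0% v 0.5% (one PT) | 3.5 v 1.8 | 6.1 |
| 4% v 2% (four such PTs pooled) | 14 v 7 | 2.4 |
| 8% v 4% | 28 v 14 | 1.9 |
| 10% v 5% | 35 v 18 | 1.7 |

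With the planned 1600 per arm, a single PT at 1.0% v 0.5% has a factor of 2.3. On these assumptions, pooling four terms at 703 patients recovers roughly the precision that one term would have had at full size.

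**4. Can a reader rebuild the grouping from the PT rows?** Not exactly. Rows count patients, and one patient may appear in several. Three rows of 8 in one arm fit any number of distinct patients from 8 to 24; three rows of 4 in the other fit 4 to 12. The rows alone therefore allow a grouped RR anywhere from (8/351)/(12/352) = 0.67 to (24/351)/(4/352) = 6.02. The SAE listing can resolve this for serious events. It does not help for the non-serious events that were collected.

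**5. What could a grouped table show?** Serious events, and non-serious events that changed treatment or ended participation. SAP 6.3 further limits the analysis to events on treatment or within 21 days after it. Respiratory infection can be expected to yield serious cases. Thrush and hoarseness, which the protocol calls localized, would seldom be captured.

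**The case against.** The strongest reply is that SAP 2.1 discloses the change and gives reasons, that the first reason is true and applies to both arms and both kinds of search, and that what remains is substantial. All of that stands. Three stronger readings should therefore be set aside.

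- A reader might infer that the summaries were dropped simply because Stiolto is well known. The text puts low patient and event numbers first.
- A reader might infer that ICS harms end up scattered over single terms, with no contrast between arms to be read. SOC totals by arm remain, counted by patient, and serious terms can be regrouped from the listing. An SOC is a pooled contrast, only a coarser one than a medical concept.
- A reader might infer that the cancelled searches would have covered each ICS harm. The documents do not list them, and Protocol 6.6 offers SMQs or custom searches as alternatives, so neither was promised individually.

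It is also fair to say that no table repairs restricted collection, and that near-empty rows for thrush and hoarseness could be misread as reassurance. That shapes the fix but does not remove the point. The figures above are constructed, and the lower limit of 1.02 should carry no weight: at an assumed 4% v 2% the risk difference runs from −0.5 to 4.5 percentage points.

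The reply does not explain why SMQs were dropped when only custom searches were called optional, or why sparse data should lead to less grouping.

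**Conclusion.** The point holds as a modest, low-cost improvement. A comparison planned in the protocol was cancelled in full on reasoning that supports only part of the cut: nothing specific is said about the SMQs, nothing about the ICS-containing arm, and the low-count argument favours grouping.

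The size cannot be stated from the documents. On assumed counts, grouping narrows the 95% factor on a risk ratio from about 6.1 to 2.4 (four terms), or the interval from 0.61–6.60 to 1.02–3.95 (three terms). Both rest on terms that do not overlap within patients and on a doubling of risk, and they show direction only.

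The SAP is Version 3.0 of March 2021 and the trial is open-label, so a reader might also infer that the cut was made in the light of results. The documents do not support that. SAP 5.0 restricts review before database lock to unpopulated table shells, and nothing says which SAP version introduced the change.

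**What to change.** In SAP 2.1, limit the cancellation to the custom searches, and state that a short ICS-related grouping is kept because it concerns the triple-therapy arm.

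In SAP 6.4.1, add one descriptive table for the safety population: number and percentage of patients, by arm, with at least one collected on-treatment AE in each grouping. Define each grouping by a named SMQ or a stated PT list, fixed before the table is populated.

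- Main row: respiratory infection, for all collected AEs and for SAEs.
- Further rows: oral candidiasis, dysphonia, osteoporosis/fracture.
- Footnote on the further rows: non-serious AEs were collected only if they led to discontinuation, dose modification or withdrawal, so low counts do not show absence of harm.

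The other custom searches can stay cancelled. No test is added.

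The cost is one table of about four rows on AE data already coded. The downside is small counts that must be read descriptively.
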